MHRA	Modern Humanities Research Association
mm	millimeter
mSv	millisieverts
OAB	Overactive Bladder
OHRP	Office of Human Research Protection
OTC	Over-The-Counter

PI	Principal Investigator
PT	Prothrombin time
PTT	Prothrombin Time Test
RUS	Renal Ultrasound
SAE	Serious Adverse Event
SBP	Systolic Blood Pressure
SDU	Scott Department ofUrology
UAE	Unanticipated Event
USSQ	Ureteric Stent Symptom Questionnaire

1. BACKGROUND

Kidney stone passage down the ureter into the bladder often results in severe abdominal pain called ureteral colic. Ureteral colic is a common presenting symptom in emergency departments (ED).

Approximately 550,000 episodes of ureteric colic are seen in ED in the United States per year costing nearly \$3 billion.¹ The current standard of care for ureteral stone passage involves hydration and pain control as approximately 47-80% of stones will pass within approximately 4 weeks, depending on size and location.² Patients who cannot achieve spontaneous stone passage or have a subsequent complication (including recurrent pain, compromised renal function, or infection) often require surgical therapy, typically either with extracorporeal shock wave lithotripsy or ureteroscopy. Two decades ago, the first randomized trial demonstrating the potential efficacy of a calcium channel blocker (nifedipine) for medical expulsive therapy of ureteral stones was performed.³ Subsequently, tamsulosin, a selective alpha-1a antagonist, has also been demonstrated as a potentially useful agent for medical expulsive therapy (MET) in randomized trials.⁴ Over the past decade, off-label MET has become more commonplace. However, the strength of findings from randomized trials is weak due to variability in quality and power of study design.

In 2015, a large multi-center randomized placebo-controlled trial (SUSPEND Trial) included 1167 patients and compared the efficacy of nifedipine and tamsulosin for the reduction in surgical therapy in patients passing ureteral stones within 4 weeks after randomization.⁵ This trial demonstrated that both nifedipine and tamsulosin were ineffective for MET and were associated with an increase in adverse effects (AE) compared to placebo. These findings suggest that current off-label therapy with calcium-channel blockers and alpha-blockers may be ineffective and inappropriate. Because ureteral stones remain an important and expensive medical problem, identification of other potential agents for MET may reduce the frequency of serious complications and necessity of surgical intervention as well as improve patient- centered outcomes.

Mirabegron is a selective beta-3 adrenergic agonist that was approved for overactive bladder in the United States in 2012. Several human and animal studies have also shown the presence of beta-3 adrenergic receptors in the ureter and efficacy of agonists for the relaxation of the ureter.^{6,7} Stimulation of the beta-3 adrenergic receptors in the human ureter have been shown to promote urothelial relaxation in a pre-clinical model.⁶ We hypothesize that mirabegron may be useful as MET through beta-3 adrenergic-mediated ureteral relaxation which may enhance ureteral stone passage in patients who are expectantly managed. Because ureteral colic results from sustained ureteric smooth muscle contraction, we hypothesize that relaxation of the ureter may reduce pain associated with ureteral stones and ureteral stents that are placed after surgical intervention.⁸ As secondary endpoints, we will assess the efficacy of mirabegron for the reduction of pain during the expectant management period and during the post- surgical stent period.

2. SIGNIFICANCE

Ureteral obstruction due to kidney stones is a common and costly condition that requires surgical intervention in 20-50% of patients. It is associated with severe pain and discomfort along with

other serious adverse health outcomes such as renal failure and sepsis. If mirabegron can reduce either the need for surgical intervention or the pain associated with ureteral colic, this may alter standard of care for expectant stone management. Furthermore, stent pain is a major common adverse sequela of surgical intervention for kidney stones.⁹ If mirabegron can reduce stent pain, it would greatly improve quality of life for patients undergoing invasive surgical therapy for urolithiasis.

3. OBJECTIVES

A. Primary Objective

The primary objective of this study is to determine whether the use of mirabegron can improve the spontaneous passage rate of patients with ureteral single ureteral calculi within 30 days of presentation.

B. Secondary Objectives

The secondary objectives of the study are to evaluate the effects of mirabegron on the reduction of pain level during the expectant management as well as stent-associated pain of those patients who had surgery.

4. DRUG INFORMATION

Mirabegron is a FDA-approved medication used in the treatment of overactive bladder (OAB) with symptoms of urgency, frequency, and leakage in adults. Both Mirabegron and placebo will be formulated and provided by Astellas Pharma US, Inc. The FDA-approved Mirabegron (50mg) product will be used without manipulation or reformulation (Mirabegron package insert; Rev. Jun 2012).¹⁰

The efficacy and safety of mirabegron have been evaluated in three 12-week studies and one long-term (12-month) safety study.

In clinical trials, mirabegron was shown to be effective in treating symptoms of OAB within the first several weeks. Those taking mirabegron made fewer trips to the bathroom and had fewer leaks than those not taking mirabegron. Results may vary.

5. PHASE OF STUDY: Phase 2

6. ELIGIBILITY CRITERIA

A. Inclusion

Subjects are eligible to be included in the study only if they meet all of the following criteria and provide signed informed consent at Visit 1.

- 1) Males and females age 18-70 years of age
- 2) Resident of Harris County
- 3) Single unilateral ureteral calculus 4 to 10 mm visible on CT scan or

- 4) Ability to tolerate oral fluids and oral pain medication
- 5) Able to make informed medical decisions regarding consent
- 6) Willingness to follow-up in the Urology Clinic in approximately 30 days
- 7) Willing to undergo ureteroscopic extraction should the stone not pass in this time period

B. Exclusion

Subjects will be excluded from the study if they meet any of the following criteria:

- 1) Adults unable to consent
- 2) Age less than 18
- 3) Solitary kidney
- 4) Horseshoe kidney
- 5) On immunosuppressant therapy
- 6) On digoxin
- 7) Uncontrolled hypertension (SBP > 170, DBP > 110)
- 8) Allergy to mirabegron
- 9) Current calcium antagonist or corticosteroid or alpha-adrenergic antagonist usage
- 10) Patients already taking a beta-adrenergic agonist medication
- 11) Patients taking thordiazine, flecainide, or propafenone (narrow CYP2D6 therapeutic index)
- 12) Renal insufficiency (GFR less than 45)
- 13) Patients with Childs B and C liver failure
- 14) Signs of infection
 - i. Temperature greater than 38C
 - ii. Circulating white blood count $>15,000 \times 10^9/L$
 - iii. Urinalysis with any of the following positive:
 - a) Positive nitrites
 - b) Positive urine culture (defined as a single isolated bacterial species population of greater than 100,000 CFU)
- 15) Patients with chronic pain already undergoing treatment with narcotic medications
- 16) Pregnant women and nursing mothers
- 17) Prisoners
- 18) No working phone number

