Subjects will be informed that they may also discontinue the study drug at any time if they would like to drop out of the trial and they may do so by contacting [name] or designee. Subjects will be informed to contact [name] or designee if they believe that they have passed their ureteral stone before discontinuing therapy. Subjects will be told to bring their medication bottles when they return to the clinic.

In the event that a subject has additional pain, discomfort, or other symptoms that may be related to their ureteral stone they may follow-up for an unscheduled visit to either the emergency department or the Urology clinic. The subject will be treated according to standard of care and information regarding their visit will be collected. If the subject must undergo an emergent procedure for their stone they will be determined to have failed therapy but will remain in the study to evaluate the study drug to reduce stent pain. Subjects that fail therapy early will undergo Visit 3 and will be evaluated at Visit 4 for the removal of their stent. Subjects will remain in the study for all outcome measurements if they do not require surgical intervention.

Interim Phone Follow-up #1 – (7 Days ± 3 days post-Visit 1)

The research study staff will contact the subject by phone approximately 7 days after Visit 1. Research staff will assess ureteral pain, medication/strainer compliance, and adverse events. Research staff will also identify whether or not the subject subjectively or objectively has passed their ureteral stone. The research staff will also answer any questions that the subject may have during this follow-up event.

Interim Phone Follow-up #2 – (21 Days ± 3 days post-Visit 1)

The research study staff will contact the subject by phone approximately 21 days after Visit 1. Research staff will assess ureteral pain, medication/strainer compliance, and adverse events. Research staff will also identify whether or not the subject subjectively or objectively has passed their ureteral stone. The research staff will also answer any questions that the subject may have during this follow-up event. The research staff will also remind the subjects to bring in their medication bottles to Visit 2 (see below).

Visit 2 – Urology Clinic (30 days ± 5 days post-Visit 1)

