15. RISKS

There are risks to any medication. However, mirabegron is a FDA-approved medication and has passed rigorous trials for safety.

- A. Mirabegron:** Mirabegron is contraindicated in patients who have known hypersensitivity reactions to mirabegron or any component of the tablet. Mirabegron can increase blood pressure. Periodic blood pressure determinations are

recommended, especially in hypertensive patients. Mirabegron is not recommended for use in severe uncontrolled hypertensive patients (defined as systolic blood pressure ≥ 180 mm Hg and/or diastolic blood pressure ≥ 110 mm Hg).

Urinary retention in patients with bladder outlet obstruction (BOO) and in patients taking antimuscarinic medications for the treatment of OAB has been reported in post-marketing experience in patients taking mirabegron. A controlled clinical safety study in patients with BOO did not demonstrate increased urinary retention in Mirabegron patients; however, Mirabegron should be administered with caution to patients with clinically significant BOO. Mirabegron should also be administered with caution to patients taking antimuscarinic medications for the treatment of OAB.

Angioedema of the face, lips, tongue and/or larynx has been reported with Mirabegron. In some cases angioedema occurred after the first dose. Cases of angioedema have been reported to occur hours after the first dose or after multiple doses. Angioedema associated with upper airway swelling may be life threatening. If involvement of the tongue, hypopharynx, or larynx occurs, promptly discontinue Mirabegron and initiate appropriate therapy and/or measures necessary to ensure a patent airway.

Since Mirabegron is a moderate CYP2D6 inhibitor, the systemic exposure to CYP2D6 substrates such as metoprolol and desipramine is increased when co-administered with Mirabegron. Therefore, appropriate monitoring and dose adjustment may be necessary, especially with narrow therapeutic index drugs metabolized by CYP2D6, such as thioridazine, flecainide, and propafenone.

Most commonly reported adverse reactions over 2% and greater than with placebo) were hypertension, nasopharyngitis, urinary tract infection and headache.

Subjects will be monitored carefully for such side effects and should the subject feel uncomfortable continuing treatment, he will be allowed to discontinue participation in the study.

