17. WITHDRAWAL OF SUBJECTS

Subjects for the study will be selected during screening based on the inclusion and exclusion criteria and clinical assessment listed below. Subjects will be discontinued from the study prematurely if:

- A. Unacceptable AEs considered by the investigator to be associated with use of the study drug occur
- B. The subject requests to be withdrawn from the study
- C. A need for concomitant medication prohibited by the protocol arises
- D. The Principal Investigator decides that it is in the subject's best interest
- E. The subject is significantly non-compliant with the protocol

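### Minor safety correction: exclusion 7 admits a patient with a diastolic pressure of exactly 110, whom Section 15 places in the group for which mirabegron is not recommended

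*Combined protocol and SAP*

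**What the plan says.** Two places in the combined protocol and SAP set blood-pressure limits.

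- **Section 6.B, exclusion 7:** "Uncontrolled hypertension (SBP > 170, DBP > 110". The list opens with "Subjects will be excluded from the study if they meet any of the following criteria", so meeting any one numbered item excludes a patient. Inside item 7 the two limits are joined only by a comma.
- **Section 15.A (risks of mirabegron):** "Mirabegron is not recommended for use in severe uncontrolled hypertensive patients", and that group is "defined as systolic blood pressure ≥ 180 mm Hg and/or diastolic blood pressure ≥ 110 mm Hg". The same paragraph states "Mirabegron can increase blood pressure" and advises periodic checks, particularly in people with hypertension.

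The rest of the plan bears on this as follows.

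- Section 8 starts dosing immediately and supplies 60 capsules.
- In Appendix A, blood pressure is recorded at Visits 1, 2, 3 and 4. Footnote 1 allows the Visit 1 reading to precede enrolment, and Visit 2 falls at day 30 ± 5.
- For the calls at days 7 and 21, Section 9 says: "Research staff will assess ureteral pain, medication/strainer compliance, and adverse events". Neither call includes a blood-pressure reading.
- Section 17 has no blood-pressure limit for stopping. The nearest provisions are unacceptable drug-related adverse events and "The Principal Investigator decides that it is in the subject's best interest".

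**The concern.** The entry criterion is the plan's only numeric blood-pressure rule that decides who receives the drug. On systolic pressure it is stricter than the caution in Section 15 (above 170, against 180 or more). On diastolic pressure it uses the same number with a looser operator, and the plan gives no reason for being more careful on one and less on the other.

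A patient at exactly 110 could therefore be randomised, under blinding, to a drug that the plan's own risk section advises against for that patient. The next scheduled reading would be about 30 days later. That interval applies to every participant and would not change if the criterion were corrected. It is mentioned only because it makes the entry limit carry more of the load.

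The bare comma is a lesser matter. Either limit alone excluding is the natural reading and is taken as intended here.

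**Working it through.** The plan states no figure to reproduce, so the check compares the two definitions and then sizes the difference.

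**Inputs**

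| Item | Value | Source |
|---|---|---|
| Excluded at entry | SBP > 170, DBP > 110 | Section 6.B, item 7 |
| Not-recommended group | SBP ≥ 180 and/or DBP ≥ 110 | Section 15.A |
| Planned enrolment | 104, allocated 1:1, so 104 / 2 = 52 on mirabegron | Sections 11 and 8 |
| Share p of otherwise eligible candidates with DBP exactly 110 | 0.1% to 1% | Assumption; not in the documents |

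**Step 1: where the definitions disagree, reading the comma as 'or'.** A patient is in the gap if (SBP ≥ 180 or DBP ≥ 110) holds and (SBP > 170 or DBP > 110) does not.

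- Failing the exclusion requires SBP ≤ 170 and DBP ≤ 110.
- With SBP ≤ 170, the systolic limb of Section 15 cannot be met, so DBP ≥ 110 is needed.
- DBP ≤ 110 and DBP ≥ 110 together give DBP = 110.

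The gap is DBP = 110 with SBP ≤ 170. In whole mm Hg, with SBP above DBP, SBP runs from 111 to 170, which is 170 − 111 + 1 = 60 pairs. This count describes the shape of the gap, not how often it occurs.

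**Step 2: the same check reading the comma as 'and'.** Exclusion would then require both SBP > 170 and DBP > 110. A patient at 165/115 or 190/100 would also be eligible, so the gap widens. The 'or' reading is the more favourable to the plan.

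**Step 3: does another criterion close the gap?** Exclusion 7 is one of 18 numbered exclusions. None of the other 17 sets a blood-pressure limit, and no inclusion criterion does.

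**Step 4: the corrected rule.** With SBP > 170 or DBP ≥ 110, a patient who is not excluded has SBP ≤ 170 and DBP < 110, and so cannot meet either limb of Section 15. The gap falls from 60 pairs to 0, and the only pairs newly excluded are those 60.

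**Step 5: how many subjects.** Expected number enrolled = 104p; expected number on mirabegron = 52p; chance of at least one on mirabegron = 1 − (1 − p)^52.

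| p | 104p | 52p | Chance of at least one on mirabegron |
|---|---|---|---|
| 0.001 | 0.10 | 0.05 | 1 − 0.999^52 = 0.051 |
| 0.005 | 0.52 | 0.26 | 1 − 0.995^52 = 0.229 |
| 0.01 | 1.04 | 0.52 | 1 − 0.99^52 = 0.407 |

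**The case against.** The strongest reply is that this is one integer on one measurement. Section 15 describes drug risks and is not an eligibility rule. Exclusion 7 does not copy it: the systolic limit differs, and the label omits the word severe, so the authors may have chosen their own limits. A patient at 109 stays eligible after the change, and nothing in the documents quantifies extra harm at 110. The upper figure of 41% comes entirely from the top of an assumed range.

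There are also softer safeguards. Section 17 refers to clinical assessment at selection as well as the listed criteria. Section 15 promises careful monitoring for side effects, hypertension being among the common ones. Section 9 allows unscheduled visits for stone-related symptoms. Section 17 provides for discontinuation.

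Most of this stands as a matter of weight. The documents do not establish intent, and the practical effect is small. It does not remove the inconsistency. The safeguards are discretionary or act after randomisation, and none makes a patient at 110 ineligible. Section 15 gives a caution and not a prohibition, but the plan offers no reason for departing from it at this one value. The monitoring interval is a separate matter and adds nothing to the size of this one.

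**Conclusion.** The concern holds and is minor. As written, exclusion 7 lets in a patient with a diastolic pressure of exactly 110 and a systolic pressure of 170 or less, and Section 15 counts that patient among those for whom mirabegron is not recommended. This follows from the text and depends on no assumption beyond the 'or' reading; the alternative reading makes the gap larger.

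The number affected does rest on an assumption. For p between 0.1% and 1%, about 0.1 to 1.0 of 104 subjects would be affected, 0.05 to 0.5 of them on mirabegron. The stricter systolic limit is protective and is not in question. It remains worth correcting because it is a safety entry threshold for a drug that can raise blood pressure, and the correction costs almost nothing.

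**What to change.** Amend exclusion 7 to: *Uncontrolled hypertension (SBP > 170 or DBP ≥ 110)*. Use the same wording on whatever eligibility form or checklist the site works from. Keep the systolic limit at 170 and leave Section 15 as it is. The word 'or' also settles the comma.

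The cost is a one-line amendment, with BCM IRB approval under Section 23.F. Candidates at exactly 110 become ineligible, about 0 to 1 per 104 under the assumed range. The sample size and analysis need no change.

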7. DESIGN

The study will be a prospective randomized double-blind placebo-controlled trial of mirabegron for MET in patients with a CT scan or Ultrasound/KUB-proven ureteral stone between 4 to 10 mm undergoing expectant management. Subjects will be distributed at a 1:1 ratio between the control and treatment groups. The treatment group will receive mirabegron and the control groups will receive a placebo. Both groups will receive analgesics and hydration will be recommended. All subjects will then be followed for 30 days to determine the proportion of subjects with spontaneous passage. Patients will record narcotic usage and pain scores during

this time. If there is stone persistence in the ureter based on imaging (CT scan or Ultrasound/KUB of the abdomen and pelvic, then the patient will undergo ureteroscopy with stent placement. In these patients, treatment will continue while the stent is in place and patients will fill out a validated questionnaire regarding stent pain.

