9. PROCEDURES

Visit 1 – Emergency Department

In the ED, the subjects will receive a full history and physical, blood tests (including CBC and BMP), urinalysis and culture, urine pregnancy test, CT scan or Ultrasound/KUB of the abdomen

and pelvis, and KUB as part of standard of care for ureteral colic. The radiology department will note on all imaging the largest diameter of the stone and the Hounsfield units. Research study staff will screen potential subjects in the ED by reviewing their charts and will obtain written and verbal consent (in Spanish when necessary) from subjects who meet all inclusion and exclusion criteria. Baseline data, including demographics, medical and surgical history, and current medications, will be collected before randomization.

Each subject will be assigned a unique, consecutive three-digit identification number (i.e., 001, 002...). The study number will be utilized for identification of the subject throughout the study. The clinical study coordinator of the trial will maintain the code that links the name of the participant to their study identification number. The study coordinator will maintain the code in a secured cabinet and the code will be kept confidential. Only the clinical study coordinator and Principal Investigator (PI) can access and view the codes.

Subjects will be asked to complete the Wong-Baker FACES pain scale (available with validated Spanish translation as well). Subjects will be discharged from the ED with a (1) 60 day prescription for the study drug (mirabegron or placebo) (2) urine strainer (3) 60 day log for recording medication adherence, narcotic/analgesic usage, and ureteral pain. Subjects will be instructed to take one pill per day beginning immediately and continuing until they have completed all pills or until they have been instructed to discontinue by the study staff.

Subjects will be provided instructions for use of the urine strainer and collection of any stone or stones that may be passed. They will be instructed to bring any stones that have been passed to the next clinic visit.

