13. DATA ANALYSIS

Patient demographics and clinical characteristics will be summarized by means with standard deviations, medians with minimum and maximum values, or frequencies with percentages. Summary statistics will be stratified by treatment group. No univariable analysis will be completed in this randomized clinical trial.

The primary analysis will compare the proportion of subjects with spontaneous stone passage within 30 days between study groups using Fisher's exact test. Statistical significance will be assessed at the 0.05 level (two-sided). A logistic regression model will also be used to estimate the odds ratio for spontaneous stone passage in the mirabegron group versus the placebo with a 95% confidence interval.

A multiple logistic regression model, adjusting for treatment group, will also be used to test for significant associations between spontaneous stone passage and patient demographics or clinical characteristics. Parameter estimates significant at the 0.05 level will be included in the final multiple regression model. No adjustments will be made for multiple hypothesis testing.

A secondary objective of this study is to compare pain measures between treatment groups. The Wong Baker FACES pain scale will be measured daily for each patient. A general linear mixed model will be used to compare pain scores between treated and placebo groups. The model will include fixed effects for treatment group, time (discrete) and a group-time interaction term. The matrix of correlated residual terms will assume an unstructured format. This model will account for the correlation between repeated measures within the same subject and will allow for all available data to be included in the model.

Missing data will not be imputed. Model fit will be assessed using influence diagnostics and residual analysis. Data transformations (e.g., natural logarithm) will be used if departure from model assumptions is evident. The model will also be used to explore associations between pain scores and demographic and clinical characteristics, adjusting for treatment group and time.

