14. END-POINTS

Endpoints will include spontaneous passage rate during the 30-day expectant management period or completion of the expectant management period without a requirement for surgery. Secondary endpoints will include ureteral pain during the expectant management period (Visit 1, Interim Follow-up #1 and #2, Visit 2) and pain with a ureteral stent in place (Visit 4).

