APPENDIX B: QUESTIONNAIRES

**A DOUBLE BLIND PLACEBO CONTROL TRIAL OF MIRABEGRON FOR
MEDICAL EXPULSIVE THERAPY AND TO MANAGE STENT PAIN FOR
URETERAL STONES (Protocol # 01-16-20-02)**

Wong-Baker FACES® Pain Rating Scale

©1983 Wong-Baker FACES® Foundation. www.WongBakerFACES.org
Wording modified for adult use. Used with permission.

You have agreed to participate in the clinical research study conducted by Dr. [name]. As part of that study, we need to review your pain levels while you are in the study. Please complete the follow diary **once a day** until you return to the clinic.

Example of completed row:

Day	DATE	Time of Day	Pain Scale	Medication for Pain (if needed)
5	2/5/16	9:30 AM	6	Aspirins x 2

Please complete the follow diary once a day until you return to the clinic.

Day	DATE	Time of Day	Pain Scale	Medication for Pain (if needed)
1				
2				
3				
4				
5				
6				
7				
8				

Subject ID# _____

Visit # _____

Page 2 of 3

Day	DATE	Time of Day	Pain Scale	Medication for Pain (if needed)
9				
10				
11				
12				
13				
14				
15				
16				
17				
18				
19				
20				
21				
22				
23				
24				
25				
26				
27				
28				
29				
30				
31				
32				
33				
34				
35				
36				

Subject ID# _____

Visit # _____

Page 3 of 3

Day	DATE	Time of Day	Pain Scale	Medication for Pain (if needed)
37				
38				
39				
40				
41				
42				
43				
44				
45				
46				
47				
48				
49				
50				
51				
52				
53				
54				
55				
56				
57				
58				
59				
60				

Wong-Baker FACES® Pain Rating Scale

www.wongbakerFACES.org

©1983 Wong-Baker FACES® Foundation. Used with permission.

A DOBLE CIEGO PLACEBO CONTROL ESTUDIO DE MIRABEGRON PARA TERAPIA MEDICA DEL MANEJO DEL DOLOR Y EXPULSION DE PIEDRAS DE LOS URETERS (Protocol # 01-16-20-02)

Usted acepto participar en un estudio de investigación clínica conducido por el Dr. [name]. Como parte del estudio, necesitamos revisar su nivel de dolor mientras usted está en el estudio.

Por favor complete el siguiente diario una vez al día hasta que usted regrese a la clínica.

Ejemplo de como completar la tabla:

Dia	Fecha	# Hora Del Dia	Escala del Dolor	Medicina para el dolor (si necesita)
5	2/5/16	9:30 AM	6	Aspirina x 2

Please complete the follow diary once a day until you return to the clinic.

Dia	Fecha	# Hora Del Dia	Escala del Dolor	Medicina para el dolor (si necesita)
1				
2				

Subjeto ID# _____

Visita # _____

Página 2 de 3

3				
4				
5				
6				
7				
8				
9				
10				
11				
12				
13				

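### The arms are compared on pain scores alone although as-needed pain medication is logged daily, so the score difference can understate any effect on pain

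*Combined protocol and SAP*

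**What the plan says.** All references are to the combined protocol and SAP.

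- **Treatment of pain.** Section 7: "Both groups will receive analgesics and hydration will be recommended". No section sets a fixed analgesic regimen for the expectant period, or a time of scoring relative to a dose.
- **Data collected.** Section 7: "Patients will record narcotic usage and pain scores during" the 30-day follow-up. Section 9, Visit 1, issues a "60 day log for recording medication adherence, narcotic/analgesic usage, and ureteral pain". The diary in Appendix B asks for one row a day ("Please complete the follow diary once a day until you return to the clinic"), with a pain score and a column headed "Medication for Pain (if needed"). Appendix A schedules a narcotics diary together with the FACES scale.
- **Objective and endpoints.** Section 3B names "the reduction of pain level during the expectant management as well as stent-associated pain". Section 14: "Secondary endpoints will include ureteral pain during the expectant management period", and pain with a stent in place. Neither names analgesic use.
- **Analysis.** Section 13: "A general linear mixed model will be used to compare pain scores between treated and placebo groups", with terms for group, time and their interaction. Stent pain is compared on USSQ pain scores.
- **The only analytic role for pain medication.** Section 12 lists analgesic intake in the expectant period among covariates that the multivariable pain analysis may include.

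**The concern.** A pain score recorded while patients may take analgesics as needed reflects both the pain and the relief. Patients in more pain are likely to take more medicine. If that medicine lowers the score they write down, part of any benefit of mirabegron appears as less medication rather than as lower scores. Similar FACES means could then reflect similar pain, or more medication in the placebo arm. The planned analysis cannot separate the two, although the diary holds the data to do so.

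At stake is the pain objective in Section 3B. The primary endpoint, stone passage, is not affected.

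**Working it through.** **1. The plan's own figure.** The documents give no variance, effect size or power for pain or analgesic use. The only design figure is for stone passage (Section 11): 45 per group, 50% v 80%, Fisher's exact test. It reproduces: exact power at 45 per group is 0.815, and 90 × 1.15 = 103.5, rounded up to 104. It does not bear on this point, except that 104 × 0.85 = 88.4 leaves about 44 per arm.

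**2. Assumed inputs (none from the documents).** 44 per arm; 30 daily scores on a 0–10 scale; mean pain before analgesia 5 (placebo) v 4 (mirabegron); between-subject SD 2; day-to-day SD 1.5; medicine taken on every day with pain of 4 or more; each such day's recorded score lowered by *r* points.

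**3. Formula.** Recorded score = pain − *r* × (1 if medicated, else 0). Averaged over days and subjects:

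recorded difference = true difference − *r* × (fraction of days medicated, placebo − mirabegron)

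Clipping at 0 and 10 reduces the true difference from 1 to about 0.95. Medicated days are 19.7 v 15.0 of 30, so the difference in fractions is 4.7 / 30 = 0.157.

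| Relief *r* | By formula | Simulated (1,000 trials) | Loss | Power of score comparison |
|---|---|---|---|---|
| 0 | 0.95 | 0.95 | – | about 64% |
| 2 | 0.95 − 0.31 = 0.64 | 0.65 | 0.30/0.95 = 32% | 64% |
| 3 | 0.95 − 0.47 = 0.48 | 0.48 | 0.47/0.95 = 49% | 61% |
| 4 | 0.95 − 0.63 = 0.32 | 0.32 | 0.63/0.95 = 66% | 50% |

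A threshold of 5 gives the same pattern. The estimate shrinks steadily, but power holds up at 2 and 3 points because relief also narrows the spread between subjects. Medicated days differ between arms with about 60% power on a rank test.

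**4. Other assumptions.** With 45 per arm, both SDs equal to 2 and a 1.5-point shift, a true difference of about 1.35 is recorded as 1.15, 0.93 or 0.75 for relief of 1, 2 or 3 points, and power stays near 0.93. Near-null scores arise only if patients medicate down to a fixed comfort level. In the setting of step 2, medicating down to about 3 or 2 leaves a difference of 0.23 (power 0.44) or 0.07 (power 0.12).

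**5. The Section 12 covariate.** Adjusting the treatment comparison for medicated days cuts the estimate from a true 0.95 to about 0.09 in the first setting. In the second it falls to 0.02–0.08, with power 0.04–0.11. The covariate lies on the path from treatment to score, so adjusting for it removes most of the effect.

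**6. Which model for the added outcome.** In these simulations the variance of medicated days is about 4.7 times the mean. With no drug effect and arm as the only term, a plain Poisson model with an offset rejects in 34–38% of trials at a nominal 5%. A negative binomial model rejects in about 1% and has only 35% power under the 1-point effect. Poisson with robust standard errors rejects in close to 5% and has about 54–60% power, similar to the rank test.

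**The case against.** The strongest case against the point has four parts.

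- **The chance of missing an effect barely moves.** With 2 or 3 points of relief, power is essentially that of unmasked scores, and medicated days are no better powered than the score. This stands. A reader might infer that the plan will report no pain benefit where one exists. The documents do not support that: it needs strong relief or medicating to a comfort level, and no section describes either.
- **The inputs are invented.** This stands too. Holding mean pain at 5 for 30 days, with medicine on 19.7 of 30 placebo days, fits poorly with Section 11, which expects about half the placebo group to pass the stone in that time. Appendix B also does not say whether the daily score is taken before or after a dose, so the lowering of the score is itself an assumption.
- **The data are not wholly unused.** A reader might infer that the medication log is ignored. Section 12 allows it as a covariate, so that goes too far. But a covariate is not a between-arm comparison, and step 5 shows that this use could hide an effect.
- **The log is not about narcotics alone.** Also true: the diary column takes any pain medicine, and its example entry is aspirin. Unrestricted use is likewise inferred, from the column heading and the absence of any stated restriction.

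What survives is that pain medication is collected daily in both arms, can respond to treatment, and is never compared between them.

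**Conclusion.** The point holds as a cheap improvement to a secondary analysis. Followed as written, the plan understates any true effect on pain to the extent that as-needed medicine lowers recorded scores and is used more in one arm. On the assumed inputs the estimate loses about one third to two thirds of its size. Power falls clearly only with strong relief, to about 50% from 64% at 4 points. The direction follows from the as-needed diary and the score-only comparison, given that medicine lowers the recorded score. The size cannot be derived from the documents.

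**What to change.** In Sections 13 and 14, before unblinding:

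1. Add a supportive secondary outcome: the proportion of completed diary days with any pain medication recorded, and separately with a narcotic.
2. Count from Visit 1 to day 30, or to any stone procedure if earlier. Section 9 keeps subjects in the study after an emergent procedure and provides post-operative analgesia at Visit 3. Without the cut-off, peri-operative medicine would be counted as medicine for colic.
3. Classify the free-text entries blind to arm.
4. Compare arms with a model that allows for overdispersion, for example Poisson with log completed days as offset and robust standard errors, with the randomisation strata as terms. Report the rate ratio with a 95% interval beside the FACES difference. A rank test is a reasonable alternative or check; a plain Poisson model is not.
5. Interpret the two results together, without a formal rule that either one differing shows an effect. Such a rule runs two unadjusted 0.05 tests, with false positives of up to about 8% in these simulations.
6. State that the main treatment comparison of pain is not adjusted for pain medication used after randomisation, and amend Section 12 to match.

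Cost: coding one diary column already collected, and one more unadjusted secondary comparison, which Section 13 already accepts in principle. No new visit, form or sample is needed, and clinical management does not change.
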